### *8.2 Longitudinal RADAI-5 measurements*

Longitudinal changes in RADAI-5 will be visualised by Loess regression. The ability of longitudinal RADAI-5 measurements to discern changes in disease activity will be assessed with reference to the published minimal detectable change in DAS28, and the EULAR response criteria.

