### 4.2 Primary objectives

1. To assess the correlation and agreement between paired DAS28 and RADAI-5 measurements
2. To assess the longitudinal responsiveness and minimal detectable change in repeated RADAI-5 measurements
3. To assess the acceptability of remote PROM capture and activity/gait/heart rate monitoring, through the use of participant questionnaires and focus groups

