### *5.4 Target recruitment size*

This is a pilot study, designed to support a future definite clinical efficacy trial. As such this pilot study is not statistically powered, but rather is intended to provide preliminary data to estimate the feasibility and acceptability of remote monitoring in patients with RA, and generate an exploratory dataset for derivation of putative digital biomarkers of arthritis activity. A target of 20 participants will be recruited to the study, based upon the limited available resources for purchasing monitoring equipment in this small pilot study.

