#### *6.4 ePROMs remote capture and review*

1. All participants will be asked to complete a RADAI-5 questionnaire via the secure online ePROMs portal once every week for the 12 week follow-up duration of the study
2. Automated weekly reminder emails will be sent via the ePROMs platform to participants to remind them to complete a RADAI-5 assessment.
3. ePROMs RADAI-5 data will be reviewed at each monthly visit, and any missing data discussed with the participant to identify any difficulties in accessing or using the ePROMs platform.

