## **8. DATA ANALYSIS**

### *8.1 Correlation between DAS28 and RADAI-5 measurements*

The correlation between paired DAS28 and RADAI-5 measurements taken at each study visit will be assessed by Pearson and Spearman correlation coefficients. DAS28 and RADAI-5 scores will also be dichotomised to binary disease activity values (e.g. high disease activity vs remission/low/moderate disease activity) based on published thresholds, and agreement between categorisation by DAS28 vs RADAI-5 scores assessed by Cohen's kappa statistic.

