#### APPENDIX D : RHEUMATOID ARTHRITIS DISEASE ACTIVITY INDEX 5 (RADAI-5)

The RADAI-5[1] is a self-completed questionnaire consisting of the following five questions, each scored on a 0-10 integer scale:

1. How active was your arthritis in the last six months? (anchors: 0 = completely inactive, 10 = extremely active)
2. How active is your arthritis today with respect to joint tenderness and swelling? (anchors: 0 = completely inactive, 10 = extremely active)
3. How severe is your arthritis pain today? (anchors: 0 = no pain, 10 = unbearable pain)
4. How would you describe your general health today? (anchors: 0 = excellent, 10 = extremely bad)
5. Did you experience joint (hand) stiffness on awaking yesterday morning? If yes, how long was this stiffness? (anchors: 0 = no stiffness, 10 = stiffness the whole day)

The mean value gives an overall “RADAI-5 score”, with validated disease activity thresholds[2]:

Disease activity	RADAI-5 thresholds
Remission	0.0-1.4
Mild	1.6 – 3.0
Moderate	3.2 – 5.4
High	5.6 – 10.0

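### Primary objective 2 names the minimal detectable change of RADAI-5, but the analysis in Section 8.2 of the protocol produces no such estimate

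*Protocol*

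**What the plan says.** Section 4.2 lists as the second primary objective: "To assess the longitudinal responsiveness and minimal detectable change in repeated RADAI-5 measurements". That asks for two things, and both are properties of RADAI-5.

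Section 8.2 is the matching analysis text and has two steps. The first is descriptive: "Longitudinal changes in RADAI-5 will be visualised by Loess regression". The second concerns "The ability of longitudinal RADAI-5 measurements to discern changes in disease activity", which "will be assessed with reference to the published minimal detectable change in DAS28, and the EULAR response criteria".

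Other parts of Section 8 name their statistics. Section 8.1 gives Pearson and Spearman coefficients and Cohen's kappa, and Section 8.4 gives median or mode and range. The primary endpoint in the study summary (Section 2) covers correlation and agreement only, so it adds nothing on MDC.

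On data, Section 6.4 asks for a portal RADAI-5 "once every week for the 12 week follow-up duration of the study". RADAI-5 is also completed at all four visits next to the DAS28-CRP components (Section 15), and Section 8.1 uses those pairs: "The correlation between paired DAS28 and RADAI-5 measurements taken at each study visit". Section 5.4 sets the size: "A target of 20 participants will be recruited to the study, based upon the limited available resources".

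**The concern.** An MDC is the smallest change in one person's score that exceeds measurement error. It belongs to a particular instrument and is expressed in that instrument's units. Section 8.2 mentions only the MDC of DAS28. A smoothed curve does not estimate measurement error, and comparison with an external criterion shows whether RADAI-5 moves when disease activity moves. Neither says how large a RADAI-5 change must be before it stands out from noise.

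The pilot is meant to support a definitive trial of remote monitoring, where weekly home scores would be read one patient at a time. The size of a change that exceeds noise is a natural thing to want from the pilot, and the protocol itself makes it a primary objective. A statistician who carries out Section 8.2 faithfully would not produce it.

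**Working it through.** **1. Objective against analysis.** The protocol states no MDC, SEM or reliability coefficient, so there is no figure to reproduce. The check is a comparison of text.

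| Part of objective 2 | Matching step in Section 8.2 | Yields an estimate? |
|---|---|---|
| Responsiveness of RADAI-5 | RADAI-5 change judged against the published DAS28 MDC and EULAR response | In principle yes; the statistic is not named |
| MDC of RADAI-5 | None; the Loess plot is descriptive and the only MDC cited is that of DAS28 | No |

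**2. Are the data there?** If complete, there are 20 × 12 = 240 weekly portal scores and 20 × 4 = 80 visit scores paired with DAS28-CRP. Pairing a portal score with the clinic score at visits 2–4 gives at most 20 × 3 = 60 pairs, clustered in 20 people. Section 6.4 fixes no portal day relative to the visit, so the number of close pairs is not secured.

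**3. Size of the missing quantity.** MDC95 = 1.96 × √2 × SEM = 2.77 × SEM. The documents give no SEM, so these values are assumptions:

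| Assumed SEM (points) | MDC95 (points) |
|---|---|
| 0.4 | 1.11 |
| 0.6 | 1.66 |
| 0.8 | 2.22 |
| 1.0 | 2.77 |

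For scale, the Appendix D bands below High span 1.4 (0.0–1.4), 1.4 (1.6–3.0) and 2.2 points (3.2–5.4). Across this range of SEM, the MDC runs from less than the narrowest of these bands to more than the widest.

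**4. Precision.** With independent errors and complete data, the relative 95% limits for the SEM, and so for the MDC, are √(df/χ²) at the 0.975 and 0.025 quantiles of χ² on df degrees of freedom.

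| Source | df | Relative 95% CI |
|---|---|---|
| 20 participants, one retest pair each | 20 | 0.77 to 1.44 |
| 5 stable participants, 4 visits | 5 × 3 = 15 | 0.74 to 1.55 |
| 10 stable participants, 4 visits | 10 × 3 = 30 | 0.80 to 1.34 |

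The counts of 5 and 10 come from Section 7.3, which expects half to three-quarters to improve: 20 × 0.25 = 5 and 20 × 0.5 = 10 would not. Some of those may worsen, so the stable group could be smaller. As an example, an MDC of 1.66 from 20 pairs would have limits of 1.66 × 0.77 = 1.28 and 1.66 × 1.44 = 2.39.

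**5. Item 1.** Appendix D shows that one of the five items asks "How active was your arthritis in the last six months". Taking six months as 26 weeks, 26 − 12 = 14 of the recalled weeks precede visit 1 at week 12. Suppose respondents average evenly over the recall period and the other four items move equally. The item then shows 12/26 = 46% of an immediate change, or half of that (23%) if the change is linear. The five-item change would be 0.8 + 0.2 × 0.46 = 0.89 or 0.8 + 0.2 × 0.23 = 0.85 of the change in items 2–5, against 0.80 if item 1 did not move. These figures depend on the assumed recall model.

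**The case against.** The strongest reply is that Section 8.2 is about responsiveness and handles it in a recognised way. The published DAS28 MDC and EULAR response tell the analyst whether disease activity changed, and RADAI-5 is judged against that. An anchor need not share the scale of the instrument being tested. This stands. A reader might infer that a DAS28 threshold will be applied to RADAI-5 scores in place of a RADAI-5 MDC; the text does not say that, and the responsiveness part is at least partly covered.

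A reader might also infer that the objective cannot be answered. That is not supported either, because the repeated scores are collected and an MDC can be calculated from them.

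The choice of estimator is often left to a statistical analysis plan, and none is shown. This stands for the formula and for the responsiveness statistic. It does not remove the mismatch, because the protocol does state an analysis for this objective and that analysis omits one of its two named quantities.

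On item 1, it would be tempting to say that it cannot follow 12-week change. Even under the simple recall model it moves by 23% to 46%, so it follows change in part. A smaller mean change also does not show poorer responsiveness, which depends on change relative to variability. The six-month question belongs to the published instrument, and the thresholds in Appendix D apply to the five-item score.

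Finally, any retest estimate here is imperfect. Participants are starting or have recently started a drug, so true change can inflate the SEM, while memory of a recent answer can deflate it. Clinic and portal entries may also differ by mode. These points limit the estimate but do not excuse its absence.

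**Conclusion.** The point holds for the MDC alone. Section 4.2 makes the MDC of RADAI-5 part of a primary objective, and Section 8.2 contains no step that yields it. Responsiveness has a usable anchor-based approach but no named statistic. Item 1 is a reason for an optional sensitivity analysis and is not an error in the plan.

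Severity is moderate. The study is a resource-limited pilot without a power calculation, and no stated figure, sample size or decision rule depends on the MDC. The comparison of objective with analysis needs no assumptions. The illustrative MDC range rests on assumed SEMs of 0.4 to 1.0, and the precision figures assume independent errors, complete data and, for the stable-group rows, 5 or 10 stable participants.

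**What to change.** Add three sentences to Section 8.2:

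- **MDC.** Estimate the RADAI-5 SEM and MDC95 = 1.96 × √2 × SEM, with a confidence interval that allows for clustering within participants. Take the SEM from repeated RADAI-5 scores over intervals in which DAS28-CRP did not change by more than its published MDC, from clinic/portal pairs within a stated short window, or from both. Fix the source and the window in advance.
- **Anchors.** State that the published DAS28 MDC and EULAR response are external anchors for responsiveness.
- **Responsiveness.** Name one statistic, for example the correlation of change in RADAI-5 with change in DAS28-CRP.

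If the sponsor does not want to estimate an MDC from 20 participants, remove it from primary objective 2 instead.

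Optionally, repeat the analysis with the mean of items 2–5 as a prespecified sensitivity analysis, keeping the five-item score as primary.

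The cost is some wording and a little extra analysis, with no new data items. The resulting MDC will be imprecise and may include mode effects or true change, and the report should say so.

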### *8.3 Digital biomarkers of disease activity*

An exploratory data-driven approach will be used to identify activity, gait and cardiorespiratory signatures that correlate with, and are predictive of, DAS28- and RADAI-5-defined disease activity levels. Continuous activity and heart rate data (evaluated with the monitoring devices) will be segmented per each day and analysed using validated (existing IP) and novel algorithms to identify activity (e.g. measure of volume, pattern and variability of walking), gait (e.g. gait speed) and heart rate (e.g. heart rate variability) digital outcomes [14].

#### *8.4 Participant acceptability*

Quantitative feedback from participant acceptability questionnaire Likert scales will be summarised (median/mode and range). Anonymised free text responses will be reproduced verbatim, analysed for common themes and presented in tabular form. Anonymised field notes from the optional focus group meeting will be explored for common themes, and summarised in a tabular form with verbatim quotes as necessary. The focus of these analyses is to gather information around participant acceptability for the purposes of improving the design of our future research studies, rather than to generate generalizable data and results suitable for a qualitative research publication.

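### The only quantitative summary named for the acceptability Likert items (median/mode and range) does not show how many participants were dissatisfied; category counts should be reported

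*Protocol*

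**What the plan says.** Section 4.2 lists acceptability as primary objective 3: "To assess the acceptability of remote PROM capture and activity/gait/heart rate monitoring, through the use of participant questionnaires and focus groups". Section 5.4 describes the pilot as "intended to provide preliminary data to estimate the feasibility and acceptability of remote monitoring in patients with RA" and sets the size: "A target of 20 participants will be recruited to the study". It gives resources as the reason for that number and states that the study is not powered.

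Section 8.4 describes the analysis in three parts.

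- Likert items: "Quantitative feedback from participant acceptability questionnaire Likert scales will be summarised (median/mode and range".
- Free text: "Anonymised free text responses will be reproduced verbatim, analysed for common themes and presented in tabular form".
- Focus group: "Anonymised field notes from the optional focus group meeting will be explored for common themes, and summarised in a tabular form".

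It then gives the purpose: "The focus of these analyses is to gather information around participant acceptability for the purposes of improving the design of our future research studies". The feedback questionnaire is completed once, at the week 12 visit (section 6.3). The focus group is optional and drawn from week 12 attendees who express interest (section 6.5). The protocol gives no acceptability threshold, and the document does not show the questionnaire's scale or items.

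**The concern.** Likert items are ordinal, usually with few levels. A median reports where the middle respondent sits, a mode reports the single most frequent answer, and a range is set by one respondent at each end. None of them says how many participants gave an unfavourable answer. For a pilot meant to estimate acceptability and shape a later study, that number is the most direct quantitative result.

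If 8.4 is followed as written, an item that nearly everyone accepted and an item that nearly half rejected could appear in the report with the same three figures. Readers planning the next study would then depend on the qualitative material to tell them apart, and that material carries no count of dissatisfied participants.

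**Working it through.** There is no figure in the plan to reproduce: the protocol states no power, threshold or expected proportion for acceptability. The check is whether the named summary can separate low from high dissatisfaction.

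**Inputs.** n = 20 (section 5.4); summary = median, mode, range (section 8.4). Assumptions, because the document does not show the questionnaire: a 5-point item, with scores 1–2 unfavourable.

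**Step 1: examples.** Counts are for scores 1, 2, 3, 4, 5. With n = 20 the median is the mean of the 10th and 11th ordered answers.

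| Counts | Unfavourable | Median | Mode | Range |
|---|---|---|---|---|
| 1, 0, 0, 18, 1 | 1/20 = 5% | 4 | 4 | 1–5 |
| 8, 1, 0, 10, 1 | 9/20 = 45% | 4 | 4 | 1–5 |
| 10, 0, 0, 9, 1 | 10/20 = 50% | 2.5 | 1 | 1–5 |

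The first two rows are indistinguishable in the planned summary. The third is not.

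**Step 2: the full span.** If 10 answers are 2 or lower, the 10th ordered answer is at most 2 and the 11th at most 5, so the median is at most (2 + 5)/2 = 3.5. A median of 4 therefore allows at most 9 unfavourable answers, and a range starting at 1 requires at least 1. Enumerating all distributions of 20 answers confirms that every number from 1 to 9 is compatible with median 4, mode 4, range 1–5. With fewer questionnaires returned the span is 1 to 8 (n = 18) or 1 to 7 (n = 16).

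**Step 3: what counts would show.** Exact (Clopper–Pearson) limits for x of n are the 2.5% quantile of Beta(x, n − x + 1) and the 97.5% quantile of Beta(x + 1, n − x).

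- 1/20 = 5%, 95% CI 0.1% to 24.9%
- 9/20 = 45%, 95% CI 23.1% to 68.5%

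**Step 4: how often the median alone stays favourable.** Suppose each answer is either favourable (4–5) or unfavourable, with true unfavourable share p. The median is favourable when at most 9 of 20 are unfavourable.

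- p = 0.30: P[Bin(20, 0.30) ≤ 9] = 0.952
- p = 0.40: P[Bin(20, 0.40) ≤ 9] = 0.755

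These figures concern the median only. They are not the probability that median, mode and range together conceal dissatisfaction.

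**Step 5: when the mode helps.** Counts of 7, 1, 0, 6, 6 give 8/20 = 40% unfavourable with median 4 but mode 1. Here the mode exposes what the median hides. The identity in Step 1 needs the favourable answers to cluster in one category.

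**The case against.** Several points against this have force.

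- **Acceptability is not assessed by these statistics alone.** Free text is reproduced verbatim and themed, and focus-group notes are themed. Section 6.5 asks for negative as well as positive experience, section 6.4 has missing ePROM entries discussed at each monthly visit, and section 9 logs people excluded by technological barriers. A reader might infer that acceptability is reduced to median/mode and range and that the pilot as a whole can miss substantial dissatisfaction. The documents do not support that. What remains is narrower: these sources can show that dissatisfaction exists and why, but the focus group is self-selected and neither it nor the free text yields the share of dissatisfied respondents.
- **The mode can move early.** A reader might infer that neither median nor mode reacts until about half the group is dissatisfied. Step 5 shows that this is untrue of the mode. The loss of information is possible, not certain.
- **The scale and cut are assumed.** This stands. It limits the numerical illustration and the favourable-proportion part of the remedy, but not the request for counts per category, which needs no cut.
- **Item tables belong in a statistical analysis plan.** An unseen plan may add counts, and nothing in 8.4 forbids them. But the protocol does not leave the matter open: it names the statistic, and someone following 8.4 would not produce counts.
- **The study is an unpowered pilot and disclaims generalisable results.** This weakens any demand for precision, and no prespecified decision turns on a proportion. It does not weaken the case for counts, which are the basic description of a small ordinal sample and serve the stated purpose of improving later studies.

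**Conclusion.** The point holds for the quantitative Likert summary. On an assumed 5-point item with 20 respondents, one and the same result (median 4, mode 4, range 1–5) is compatible with 1 to 9 unfavourable answers, that is 5% to 45%. The summary fixed in 8.4 therefore does not deliver the share that an estimate of acceptability calls for, and the qualitative analyses do not supply it.

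This is a worthwhile reporting improvement to a primary objective, not an error that undermines the study. Median, mode and range are valid descriptives for ordinal data, and nothing in the protocol is contradicted. The need for counts follows from what the three statistics measure. The size of the ambiguity rests on the assumed scale, the assumed cut and the number of questionnaires returned.

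**What to change.** In section 8.4, state that for every Likert item the report will give the number of participants answering and the n (%) in each response category. The median may stay as an additional summary. The number answering matters because the questionnaire is given only at week 12, and section 6.7 allows a device to be omitted when it is unavailable, so denominators may fall below 20.

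As a secondary addition, where the questionnaire's items and scale allow it, give the proportion with a favourable response and its exact 95% confidence interval, separately for ePROMs and for each wearable device. The favourable categories should be defined before the responses are seen.

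The cost is a sentence or two and a slightly longer table. No extra data, visits or participant burden are involved. The intervals will be visibly wide at n = 20 (9/20 gives 23.1% to 68.5%), which is a fair picture of what a pilot of this size can say.

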### **9. ETHICAL CONSIDERATIONS**

Participants will be required to attend for face-to-face hospital visits on four occasions during study follow-up. To avoid additional study visits beyond standard clinical care, we have incorporated DMARD blood safety tests within the study visit schedule. This will avoid additional trips to hospital, with potential for increased COVID-19 infection risk.

The use of an online ePROMs portal requires a computer or mobile device, internet access, and a modest degree of digital literacy to access the webpage interface. We recognise that these requirements may have an indirect effect of excluding participants of certain socioeconomic backgrounds from participating in the project. However, alternative methods of data capture (such as paper forms) are not feasible owing to the frequency of ePROMs assessments and the need to link these in real time to DAS28 and activity tracker data. Furthermore, a specific aim of this pilot project is to assess the acceptability and feasibility of internet-based ePROMs capture, to guide decisions on use in future larger studies. The screening log for this study will record where participants were unable to participate due to technological barriers, to ascertain if this is likely to be a significant barrier to recruitment to future studies and thus guide the need for future mitigation strategies.

### **10. DATA HANDLING AND RECORD-KEEPING**

#### *10.1 Collection and storage of study data*

Personal identifiable data will be stored within Newcastle upon Tyne Hospitals NHS Foundation Trust. Personal identifiable data will be removed before data transfer of link-anonymised data to Newcastle University.

1. Personal data (i.e. participant name and signature) will be recorded on paper consent forms stored within the Trial Master File.
2. Hospital number and name of participant's consultant will be stored along with study participant identification number within a paper record held in the Trial Master File, and in an electronic file on a password-protected server of the Newcastle upon Tyne Hospitals NHS Foundation Trust. This will act as a decoder for the link-anonymised data.
3. Case report forms, participant questionnaires and focus group field notes will be captured in paper format which will be held in the Trial Master File. Case report forms may then be transcribed to an electronic file which will be stored on a password-protected server of Newcastle University. Case report forms transcribed to University servers will have personal

identifiable information except sex and age removed, and be link-anonymised by trial participant number.

